### **9.1.2 Sensitivity and Supporting Analyses**

The primary analysis will be followed by two sensitivity analyses to investigate the impact of missing data on the treatment estimates. Additionally, a MAR mixed model will be reported for reference.

#### **9.1.2.1 ‘Other’ Dropouts as MNAR**

This sensitivity analysis will be a repeat of the primary efficacy analysis, but including participants that have ‘other’ marked as the reason for drop out included with the dropouts reasons to be imputed under the MNAR assumption (imputed values based on the baseline distribution).

#### **9.1.2.2 All dropouts as MNAR**

This sensitivity analysis will be a repeat of the primary efficacy analysis, but imputing all dropouts under the MNAR assumption with values based on the baseline distribution.

#### **9.1.2.3 MAR Mixed Model Repeated Measures**

This analysis will be identical to the primary analysis, but will not include the MI stage described above.

### **9.1.3 Graphical Representations**

The percent of participants reaching varying levels of improvement in CAPS-5 will be displayed in several manners. For each, the percent of participants will be out of all participants in the mITT population; thus, missing participants will be considered to have no improvement. All graphs will be produced with separate bars/lines for each treatment.

First, a continuous responder graph will be produced with percent improvement to Week 12 on the X-axis and the percent of participants achieving that level of improvement on the Y-axis. The X-axis will start at 0, so the Y intercept represents participants with any improvement; because the X-axis starts at zero and percentages are reported out of the mITT population, those with worsening/no improvement and those with missing data will be grouped together and their frequency represented by the Y intercept.

Secondly, a similar graph will be produced, but substituting the absolute change from baseline for percent improvement, again with X-axis starting at 0, so the Y intercept represents subject with any improvement; those with worsening/no improvement and those with missing data will be grouped together.

Additionally, a bar chart will be presented showing the percent of participants in 10-point groupings of Week 12 CAPS-5 scores. Percent of participants with missing data will be reported.

Finally, a bar chart will be presented showing the percent of participants in 10-point groupings of Week 12 change from baseline CAPS-5 scores. Those with worsening/no improvement and those with missing data will be presented as separate groups and the percent reported.

## 9.2 Secondary Efficacy Analysis

### 9.2.1 Continuous outcomes

The analyses of continuous secondary endpoints will be analyzed using an MMRM model identical to the primary endpoint, however, there will be no multiple imputation applied. These endpoints will include:

- CGI-I score.
- Change from baseline in SDS total.
- Change from baseline in participants' quality of sleep using the PROMIS Sleep Disturbance scale.
- Change from baseline in the disruption of work/school activities assessed using the SDS.
- Change from baseline in disruption of social life/ leisure activities assessed using the SDS.
- Change from baseline in the disruption of family life/home responsibilities assessed using the SDS.
- Change from baseline in CAPS-5 Arousal and Reactivity (Criterion E).
- Change from baseline in CAPS-5 Intrusion symptoms (Criterion B).
- Change from baseline in CAPS-5 Negative Cognition and Mood (Criterion D).
- Change from baseline in CAPS-5 Persistent Avoidance (Criterion C).
- Change from baseline in CAPS-5 Sleep Disturbance (item E-6).
- Change from baseline in CAPS-5 Exaggerated Startle (item E-4).
- Change from baseline in CAPS-5 Reckless or Self-Destructive Behavior (item E-2).
- Change from baseline in CAPS-5 Depersonalization (item 29).
- Change from baseline in CAPS-5 Derealization (item 30).
- PGIC score.
- Change from baseline in BDI-II score.

The model will be changed to include the corresponding baseline value of the secondary endpoints instead of baseline CAPS-5. Randomized participants who have a baseline and at least one post-baseline assessment for the endpoint being analyzed will be included in the model. To estimate the difference between the treatment arms in CGI-I and PGIC scores (which do not have baseline assessments), the same method will be used, however, with the observed baseline response and associated interactions removed from the list of covariates. All visits will be included in the analysis. P-values from these comparisons will be considered nominal (conclusions from the sequential testing algorithm will be

reported separately).

For each outcome, descriptive statistics (mean, SD, median, minimum and maximum) will be reported as well as LS means, standard error (SE) and p-values comparing the treatment and placebo arms at each visit. The time point of primary interest for all the above outcomes will be 12 weeks. In addition, for the SDS, the frequency of participants not working or attending school due to reasons unrelated to PTSD will be reported overall and within each visit.

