The LEC-5, which documents the patient's lifetime traumatic experiences, will be completed by the patient at Screening Visit 1 before the clinician administered CAPS-5. The CAPS-5 rater will be responsible for reviewing the answers on this form with the patient as part of the completion of the CAPS-5 Criterion A - Assessment Form in order to determine if the traumatic experience qualifies the patient for inclusion in the study. NOTE: If worst month lifetime PTSD symptoms resulted from earlier trauma(s), such as trauma(s) before age 18 or trauma(s) not related to military services, the prospective patient should be excluded from participation.

At Screening, the total CAPS-5 score (Diagnostic version with 1-month recall) must be ≥ 33 and must meet the other diagnostic criteria specified in Inclusion Criterion 2 ([Section 8.2](#)) in order for the patient to continue. At Baseline (Visit 2), the total CAPS-5 score (past week recall) must again be ≥ 33 .

The CAPS-5 interview must be completed by a qualified and trained rater. This rater should be kept consistent for a given patient throughout the study. If circumstances require non-conformity with the single rater approach for any patient, this should be documented. Additional information regarding the conduct, rating, and scoring of the CAPS-5 instrument as well as the requirements for rater training will be provided separately.

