13.4.3. Secondary Efficacy Analyses

MMRM methodology will be utilized for the continuous secondary endpoints, and analyses will be based on the mITT population. The dependent variable will be the observed change from baseline in the respective secondary endpoint at each post-randomization visit, with the exception of the CGI-I which does not have a baseline. Covariates in the model will include the fixed categorical effects of treatment, site, sex, current tobacco use status, presence of current MDE, visit and treatment by visit interaction (baseline score and baseline score by visit interaction will be included as appropriate).

Binary data will be analyzed using a Cochran-Mantel-Haenszel test controlling for the randomization stratification of presence of current MDE, analyzed separately at each visit. Patients with missing data will be analyzed as though they are non-responders. The primary time point of interest will be Week 12. Odds ratios and corresponding 95% confidence intervals will be presented.

To adjust for multiplicity and to control for overall type I error, a sequential test procedure will be applied to the key secondary efficacy endpoints. If the primary analysis produces a result that is statistically significant, a nominal significance level will be used for comparing the secondary endpoints in an ordered fashion. If the analysis for a secondary endpoint does not produce a statistically significant result, then the remaining secondary endpoint analyses will automatically be considered non-significant regardless of the p-value produced. In the case of an early stop or increase in sample size, the same methodology/critical value used for the primary endpoint will be applied to the key secondary endpoints for the purposes of the sequential testing. See the SAP for additional details.

The testing order for the two key secondary endpoints is as follows:

- CGI-I score (analyzed as a continuous variable) after 12 weeks of treatment.
- Change from baseline in the SDS total score after 12 weeks of treatment.

No other adjustments for multiplicity will be made and other p-values displayed in the output will be considered for descriptive summary purposes only and will not be used for formal inference. Full details regarding the statistical analyses for the listed endpoints will be provided in the SAP.

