## 6. ANALYSIS POPULATIONS

The following analysis populations are planned for this study:

- **Safety Population (SAFETY):** All participants who receive at least 1 dose of study drug. Participants who are issued study drug, but return 100% of it (i.e., none consumed) will be excluded from the safety population; likewise participants that have no follow up following receipt of study drug to indicate they took drug are excluded. All safety analyses and demographic/baseline characterization will be performed using this population, analyzed as treated; participants will be summarized under TNX-102 SL 5.6 mg if they were issued it at any visit (including participants that are rolled over to open-label TNX-102 SL 5.6 mg in the case of an early stop recommended by the IDMC during the planned interim analysis).
- **Modified Intention-to-Treat Population (mITT):** All randomized participants who have at least a baseline and one post-baseline CAPS-5 assessment. This is the primary population for efficacy analyses and participants will be analyzed based on their randomized treatment.
- **Early Stop Safety Population (SAFETY):** This population is identical to the safety population but is limited to only the participants that are part of the interim analysis, (i.e. participants that are ongoing at the time of early stop are excluded). In the case of an early stop, safety results will be analyzed on both safety populations. Should the study continue to full enrollment (or full enrollment on an increased sample size), this population will not be utilized.
- **Early Stop Efficacy Population (mITT):** This population will be limited to those participants who are part of the interim analysis, i.e., among the approximately 275 patients defined as the population upon which the predefined interim analysis efficacy assessments will be conducted. Only those participants who have a baseline and at least one post-baseline CAPS-5 assessment will be evaluated for purposes of the interim analysis. Participants will be analyzed based on their randomized treatment. The dataset for this population will be defined by the completion or early termination of the last participant among this cohort.

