#### **7.1.1 Adjustments for Multiplicity and Other Alpha Control**

##### **7.1.1.1 Multiplicity**

To adjust for multiplicity and to control for overall type I error, a fixed sequence procedure will be applied to key secondary efficacy endpoints. If the primary analysis produces a result that is statistically significant at a given level, the key secondary

endpoints will be tested in an ordered fashion at the same level. If the analysis for a secondary endpoint does not produce a statistically significant result, then the remaining secondary endpoint analyses will automatically be considered non-significant regardless of the p-value produced. In the case of an early stop or increase in sample size, the same methodology/critical value used for the primary endpoint will be applied to the key secondary endpoints for the purposes of the sequential testing.

The order in which the key secondary endpoints, intended for labeling purposes, will be tested is as follows:

- i. CGI-I score after 12 weeks of treatment (as a continuous outcome)
- ii. Change from baseline in the SDS total score after 12 weeks of treatment.

No other adjustments for multiplicity will be made and other p-values displayed in the output will be considered for descriptive summary purposes only and will not be used for formal inference. Additional details regarding statistical analysis for the listed endpoints can be found in [Section 9.2](#).

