#### 7.1.1.2 Alpha Spend, Early Stops and Sample Size Increase

[REDACTED]

In the case of a sample size increase, the same inverse-normal method described in the primary efficacy analysis will be applied to the key secondary analyses to adjust the reported p-value; these will be tested at one-sided [REDACTED] to account for the first stage alpha spend.

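### CGI-I, the first key secondary endpoint, and PGIC are modelled without baseline CAPS-5, although every participant has it; adding it is a nearly free gain in precision

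*SAP*

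**What the plan says.** **Baseline covariate.** The primary MMRM (SAP 9.1.1) includes baseline CAPS-5 and its interaction with visit. For the continuous secondary endpoints, SAP 9.2.1 states: "The model will be changed to include the corresponding baseline value of the secondary endpoints instead of baseline CAPS-5". For CGI-I and PGIC, which are not measured at baseline, the same model is used "with the observed baseline response and associated interactions removed from the list of covariates". Protocol 13.4.3 is more open: "baseline score and baseline score by visit interaction will be included as appropriate".

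**Availability.** Protocol 11.2.1 makes the Visit 2 score an entry condition: "At Baseline (Visit 2), the total CAPS-5 score (past week recall) must again be" at least 33. The mITT definition in SAP 6 also requires it: "All randomized participants who have at least a baseline and one post-baseline CAPS-5 assessment".

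**Role of the endpoints.** SAP 7.1.1.1 introduces the sequence with "The order in which the key secondary endpoints, intended for labeling purposes, will be tested is as follows". CGI-I, as a continuous score, comes first and SDS total second. PGIC is not in the sequence.

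**Missing data.** SAP 9.1.1 imputes CAPS-5 by reason for discontinuation. After lack of efficacy, loss to follow-up or an adverse event, values are drawn from the baseline distribution, conditional on observed post-baseline values. SAP 9.1.2 adds two analyses that widen that rule. The continuous secondary endpoints get an "MMRM model identical to the primary endpoint, however, there will be no multiple imputation applied". SAP 9.1.2.3 calls the corresponding CAPS-5 model a missing-at-random (MAR) model.

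**The concern.** The CGI-I rating is an investigator's judgement of change, made with the other assessments at hand. How much a participant can improve, or is judged to have improved, may depend on starting severity. If so, adjusting for baseline CAPS-5 removes outcome variance that otherwise stays in the error term. The SAP drops the covariate because CGI-I has no baseline of its own, but that is no reason to drop the baseline severity measure that does exist. At stake is some precision on the first endpoint after the primary; if CGI-I misses significance, SDS total cannot be claimed either.

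A smaller, related matter is SDS total. It is intended for labeling, yet its only analysis assumes MAR. A reader could not see whether its result holds under the dropout assumption that the sponsor itself adopts for the primary endpoint.

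**Working it through.** **What the documents supply.** There are 550 participants in 2 arms (550/2 = 275 per arm), an interim at about 275 participants in total, and about 45 sites. The point disputes no figure. The visible text gives no effect size, SD, power, dropout rate or correlation, so those inputs below are assumptions.

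**Covariates left in the CGI-I and PGIC models.** Treatment, site, sex, tobacco use, current MDE, visit and treatment by visit. None of them measures PTSD severity.

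**Gain from adding baseline CAPS-5.** Let r be its correlation with Week 12 CGI-I within arm. The variance falls by r². With 80% power assumed at two-sided 0.05, power becomes Φ((1.960 + 0.8416)/√(1 − r²) − 1.960).

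| r | Variance reduction | Power |
|---|---|---|
| 0 | 0% | 80.0% |
| 0.1 | 1% | 80.4% |
| 0.2 | 4% | 81.6% |
| 0.3 | 9% | 83.6% |

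**Allowing for overlap.** Assume a correlation of 0.3 between baseline CAPS-5 and the other covariates, and of 0.2 between those and CGI-I. The partial r² is ((r − 0.3 × 0.2)/√(0.91 × 0.96))², which is 0.2%, 2.2% and 6.6% at r = 0.1, 0.2 and 0.3. The same power formula then gives about 80.1%, 80.9% and 82.6%. The entry cut-off of 33 narrows the baseline range and tends to lower r further.

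**Cost if the covariate is useless.** The variance inflation is roughly 1/(n − p − 2). Here p = 49: 44 site terms, treatment, sex, tobacco, MDE and the added covariate. At n = 550 this is 1/499 = 0.2%. At n = 275, the size of one planned stage, it is 1/224 = 0.45%.

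**SDS total: how much the missing-data assumption could matter.** Early-termination values go to the nearest visit (SAP 7.1.2), with midpoints at Days 42 and 70. If such visits were spread evenly over Days 11 to 84, (70 − 11)/73 = 81% would still leave Week 12 missing.

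Assume Week 12 improvement of 8 (active) against 6 (placebo), a difference of 2.0, and zero change in the reason-based dropouts. The difference becomes (1 − pA) × 8 − (1 − pP) × 6, where pA and pP are the dropout shares:

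- 10%/10%: 7.20 − 5.40 = 1.80 (−10%)
- 12%/8%: 7.04 − 5.52 = 1.52 (−24%)
- 8%/12%: 7.36 − 5.28 = 2.08 (+4%)

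These percentages compare with an MMRM estimate that stays at 2.0, which happens only if earlier observations carry no information. Suppose instead that completers are at 7 and 5.25 at Week 8, dropouts are seen there with zero change, and the Week 8 to Week 12 slope is b. The MMRM then places dropouts at 8 − 7b (active) and 6 − 5.25b (placebo):

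- b = 0.5: dropouts at 4.50 and 3.375. At 12%/8% the MMRM gives (7.04 + 0.54) − (5.52 + 0.27) = 1.79, and 1.52 is 15% below it.
- b = 0.7: dropouts at 3.10 and 2.325. At 12%/8% it gives (7.04 + 0.372) − (5.52 + 0.186) = 1.71, and 1.52 is 11% below it. At 10%/10% it gives (7.20 + 0.31) − (5.40 + 0.2325) = 1.88, and 1.80 is 4% below it.

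The −24% is therefore an upper-end figure for its dropout pattern.

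**The case against.** **On the covariate.** The omission is explicit and agrees with the protocol, which notes that CGI-I has no baseline and leaves baseline terms to judgement. No error rate is affected, and the gain may be close to zero. The change would also alter the main model of an endpoint under type I error control, in a SAP sent to FDA together with the interim plan, the IDMC charter and the simulation report. All of this stands as a limit on importance and on timing. It does not count against the change itself: the protocol wording permits it, the data are already collected, and the worst case is a fraction of one percent of variance.

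**On SDS total.** Confining reason-based imputation to the primary endpoint is a legitimate prespecified choice. SDS is tested only after CAPS-5 and CGI-I have both succeeded. Early-termination visits from Day 11 collect CAPS-5 and SDS together (protocol 10.5.1), so the CAPS-5 analyses stress largely the same dropouts. A supportive analysis would not change the tested SDS result. This largely stands, and it is why the SDS item is only a suggestion. What remains is that robustness of a clinician-rated scale does not show robustness of a self-reported one. CGI-I has a responder analysis that counts missing as non-response (SAP 9.2.2), while SDS has nothing comparable.

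**Stronger readings that the documents do not support.** A reader might infer that imputation was promised for the key secondary endpoints and then withdrawn. The carry-over of methodology in SAP 7.1.1.1 concerns sequential testing after an early stop or a sample-size increase. The seeds that SAP 14.3 allots to secondary endpoints specify no imputation; they are a loose end. A reader might also take the −24% as a forecast for SDS. It rests on assumed dropout rates and on earlier data being uninformative.

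**Conclusion.** The point holds as a low-cost improvement. The CGI-I and PGIC models carry no severity covariate although one exists for every mITT participant. Under assumed correlations of 0.1 to 0.3 the gain is 0.4 to 3.6 points on an assumed 80% power, and about 0.1 to 2.6 points with the assumed overlap. The downside is about 0.2% to 0.45% of variance. It would be wrong to infer bias or an inflated type I error: randomization protects the comparison with or without the covariate.

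The SDS item is secondary and optional. SDS total is analysed only under MAR, but neither the size nor the direction of any change under another assumption can be determined from the documents. SAP 7.1.1.2 is partly redacted and the interim plan is not among the documents; nothing visible points to an SDS analysis there.

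**What to change.** **Main change, SAP 9.2.1.** Add baseline total CAPS-5 and its interaction with visit to the CGI-I and PGIC MMRMs. Fix this before any unblinded analysis; if unblinding has already occurred, report the adjusted model as supportive only. The cost is one covariate with its interaction, no new data, and an amendment to the main model of the first key secondary endpoint. Testing order and alpha are unchanged.

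**Optional, SDS total.** Keep the MMRM without imputation as the main analysis and add one supportive reason-based analysis:

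- Use the SAP 9.1.1 imputation with baseline SDS total in place of baseline CAPS-5, conditional on observed post-baseline SDS.
- Use the SAP 9.2.1 analysis set: a baseline and at least one post-baseline SDS.
- Impute the 0–30 total after the work/school rescaling of SAP 7.2.3.2, so that a change in work status needs no separate rule.
- If the sample size is increased, run it by stage, in line with SAP 7.1.1.2, where "the same inverse-normal method described in the primary efficacy analysis will be applied to the key secondary analyses".

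The cost is one extra analysis, whose estimate may be less favourable than the main one.

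**Housekeeping.** Reconcile the seeds for secondary endpoints in SAP 14.3 with the statement in SAP 9.2.1 that no imputation is applied to them.

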### 9.2.2 Categorical outcomes

Binary data over time will be analyzed using a Cochran Mantel Haenszel (CMH) test stratified by presence of current major depressive episode. Examples include the CGI-I and the PGIC, in which responders are defined as those who score '2' (much improved) or '1' (very much improved) on these 7-point scales. Participants with missing data will be analyzed as though they are non-responders. This will be reported for each visit with the primary time point of interest at Week 12 (with remission spanning data at weeks 8 and 12). Odds ratios for treatment contrasts along with two-sided 95% CIs will also be reported. Two-sided p-values for the test of no difference between the TNX-102 SL and placebo will be provided.

These endpoints will include:

- Proportion of participants with a PGIC score of "much improved" or "very much improved".
- Proportion of participants with a CGI-I score of "much improved" or "very much improved".
- Proportion of participants with a Total CAPS-5 score of 0–10 (asymptomatic/few symptoms).
- Proportion of participants with a Total CAPS-5 score of 0-22 (asymptomatic or mild PTSD/subthreshold).
- Proportion of participants with Response, defined as a  $\geq 10$ -point improvement from baseline in Total CAPS-5 score.
- Proportion of participants with Loss of Diagnosis, defined as Response AND no longer meeting DSM-5 symptom criteria in any one or more of the four clusters (B, C, D, E).
- Proportion of participants in Remission, defined as Loss of Diagnosis AND Total CAPS-5 score  $\leq 10$ .
- Proportion of participants achieving sustained Remission, defined as Loss of Diagnosis AND Total CAPS-5 score  $\leq 10$  after both 8 weeks AND 12 weeks of treatment.
- Proportion of participants with a  $\geq 50\%$  improvement from baseline in Total CAPS-5 score.

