#### **3.2 Method of Treatment Assignment and Randomization**

Once all pre-randomization assessments have been completed, only those participants who meet all of the following randomization criteria will be eligible to continue:

1. Participant continues to meet all inclusion and exclusion criteria, including urine and blood test results, and
2. Visit 2 total CAPS-5 score  $\geq$  33 (“Symptom Severity” version using 1-week recall), and

3. At Visit 2, participant is not severely depressed (based on the investigator's judgment and Visit 2 C-SSRS, CAPS-5, and BDI-II, and considering the pre-randomization collaborative review by the investigator and medical monitor(s) of the participant's Visit 1 psychiatric history, presenting symptomatology, MINI 7.0.2, C-SSRS, CAPS-5, and BDI-II assessments).
4. No active suicidal intent or plan, based on Investigator's judgment, and Visit 2 C-SSRS responses (e.g., no C-SSRS Type 4-5 ideation or suicidal behavior since Visit 1).

If the participant meets all study randomization criteria, they will be randomly assigned in a 1:1 ratio to receive placebo or TNX-102 SL 5.6 mg for 12 weeks. A dynamic randomization procedure will be employed at Visit 2 to minimize trial-wide imbalances between the treatment groups for site, sex, current tobacco/nicotine use (yes/no) and presence (yes/no) of current MDE based on the MINI conducted at Visit 1.

Treatment A: 2 x TNX-102 SL 2.8 mg tablets ("TNX-102 SL") to be taken sublingually once daily at bedtime.

Treatment B: 2 x placebo tablets ("placebo") to be taken sublingually once daily at bedtime.

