For maximum statistical efficiency, the weights are defined prospectively according to the square-root of the planned proportion of participants in the two stages, relative to the preplanned total enrollment of 550 participants, as  $w_i = \sqrt{0.5}$ . The calculation of these weights is fixed and will not be changed due to unblinded data and is hence in line with the draft guidance on adaptive design clinical trials (CDER, CBER, February 2010). In order to control the type-I error, adaptive changes of the stage wise sample sizes will not lead to changes of the weights (Lehmacher & Wassmer 1999).

A Mixed Model Repeated Measures (MMRM) analysis will be performed for the change from baseline in CAPS-5 total score to estimate the treatment difference at Week 12. The model will include all participants in the mITT population, and the dependent variable will be the observed change from baseline in total CAPS-5 score at each post-randomization visit. Covariates in the model will include the fixed categorical effects of treatment, site, sex, current tobacco use status, presence of current MDE, visit and treatment by visit interaction, as well as the continuous fixed covariates of baseline score and baseline score by visit interaction. An unstructured covariance matrix will be used to model the within-subject variance-covariance errors. The Kenward-Roger approximation will be used to estimate the denominator degrees of freedom. Should the unstructured model fail to converge, an autoregressive AR(1) covariance structure will be attempted, then finally compound symmetric should AR(1) not converge.

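### The responder analyses leave out baseline CAPS-5, which gives up a small amount of precision for the CAPS-5 0-22 endpoint

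*SAP*

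**What the plan says.** SAP 9.2.2 lists nine binary endpoints and specifies a CMH test "stratified by presence of current major depressive episode". Missing data count as non-response, and odds ratios with 95% intervals are reported. Protocol 13.4.3 gives the same test, "controlling for the randomization stratification of presence of current MDE, analyzed separately at each visit", and the efficacy part of the protocol synopsis agrees.

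Allocation uses more than MDE. SAP 3.2 describes a dynamic procedure that balances the arms "for site, sex, current tobacco/nicotine use (yes/no) and presence (yes/no) of current MDE", and Protocol 7.1 lists the same four factors.

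The primary model (SAP 9.1.1) contains "fixed categorical effects of treatment, site, sex, current tobacco use status, presence of current MDE, visit and treatment by visit interaction" and also "continuous fixed covariates of baseline score and baseline score by visit interaction". SAP 9.2.1 carries this model over to the continuous secondary endpoints, each with its own baseline. For CGI-I and PGIC, which have no baseline, the baseline terms are removed.

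SAP 6 makes a baseline CAPS-5 a condition of entering the mITT population. SAP 7.1.1.1 places all nine binary endpoints outside the fixed sequence and treats their p-values as descriptive.

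**The concern.** Several binary endpoints are cut-offs on the Week 12 CAPS-5 total, and how far a participant must improve to reach a fixed cut-off depends on where that participant started. Randomisation requires a total of at least 33. To reach 22, someone starting at 33 must fall by 33 - 22 = 11 points, and someone starting at 60 by 60 - 22 = 38. Stratifying by MDE does not capture this directly. The documents give no reason for dropping a covariate that is always available and already in the primary model.

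At stake is precision in a descriptive secondary result that readers will use to judge clinical benefit.

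**Working it through.** **The plan's own figure.** The planned size is 550, or 275 per arm. It cannot be reproduced, because the supporting text in Protocol 13.2 is redacted and SAP 5 gives no effect, SD, rates or power. As a reference only, take assumed rates of 45% and 57%. The pooled SE is √(2 × 0.51 × 0.49/275) = 0.0426 and the unpooled SE is √((0.45 × 0.55 + 0.57 × 0.43)/275) = 0.0423. Power is Φ((0.12 - 1.96 × 0.0426)/0.0423) = 0.805.

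**Methods compared.**
- CMH: z = Σ(a_k - n_1k r_k/N_k) / √Σ[n_1k n_0k r_k (N_k - r_k) / (N_k²(N_k - 1))], summed over strata k.
- Logistic regression on treatment, MDE, sex, tobacco use and baseline CAPS-5, with a Wald test. The standardised risk difference is the mean over participants of the predicted risk on active minus the predicted risk on placebo.

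**Simulation on the CAPS-5 scale.** None of the inputs beyond 275 per arm and the threshold of 33 is in the documents. The 3,000-trial set assumes a difference of 4.5 points, residual SD 11, 20% missing counted as failures, baseline N(46, 8) truncated at 33, MDE 35%, tobacco 40% and female 15%. The 1,200-trial set is built in the same way, with a placebo mean change of -14. The 1,500-trial set also uses assumed inputs. The slope is that of the Week 12 score on baseline.

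Power (%) for CAPS-5 0-22:

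| Trials per scenario | Slope | CMH by MDE | Adjusted for baseline | Gain |
|---|---|---|---|---|
| 3,000 | 0.7 | 76.6 | 78.9 | 2.3 |
| 3,000 | 1.0 | 71.4 | 76.7 | 5.3 |
| 1,200 | 0.5 | 81.5 | 82.3 | 0.8 |
| 1,200 | 0.7 | 76.8 | 79.3 | 2.5 |
| 1,200 | 1.0 | 73.2 | 78.3 | 5.1 |
| 1,500 | 0.5 | 81.5 | 82.9 | 1.4 |
| 1,500 | 0.7 | 79.1 | 82.2 | 3.1 |
| 1,500 | 1.0 | 75.2 | 78.3 | 3.1 |

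In the 1,500-trial set the variance of the risk difference is 4-10% larger without the adjustment.

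Power (%) for other endpoints, CMH v logistic (1,200 trials):

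| Endpoint | Slope 0.5 | Slope 0.7 | Slope 1.0 |
|---|---|---|---|
| 10-point Response | 70.4 v 70.4 | 73.0 v 72.4 | 74.3 v 73.9 |
| 50% improvement | 85.2 v 85.0 | 85.0 v 85.3 | 82.8 v 84.2 |
| CAPS-5 0-10 | 40.1 v 36.9 | 40.8 v 39.5 | 44.2 v 44.0 |

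The null result for Response is expected. At slope 1.0 the change score does not depend on baseline at all.

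The CAPS-5 0-10 result carries over to Remission. Meeting all four symptom clusters needs one B, one C, two D and two E items at 2 or more, a total of at least 2 + 2 + 4 + 4 = 12. With baseline at 33 or above, a Week 12 total of 10 or less is therefore always both Response and Loss of Diagnosis.

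**How the gain depends on the correlation.** A separate latent-variable simulation (2,000 runs; 45% v 57%; Monte Carlo error about ±1.8 points on each power) varied the correlation of response with baseline:

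| Correlation | CMH by MDE | Logistic | Variance ratio of risk difference |
|---|---|---|---|
| 0 | 0.810 | 0.807 | 1.00 |
| 0.1 | 0.814 | 0.812 | 1.00 |
| 0.2 | 0.820 | 0.835 | 1.04 |
| 0.3 | 0.788 | 0.824 | 1.05 |
| 0.4 | 0.809 | 0.855 | 1.13 |
| 0.5 | 0.790 | 0.861 | 1.20 |

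To link the two scales, the truncated baseline has SD about 7.2. Slope 0.7 gives a correlation of 0.7 × 7.2/√((0.7 × 7.2)² + 11²) ≈ 0.42, and slope 1.0 gives 7.2/√(7.2² + 11²) ≈ 0.55. The CAPS-5-scale gains are somewhat smaller at these values, plausibly because missing values counted as failures dilute them.

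**The other allocation factors.** Adding sex and tobacco as CMH strata gives 75.7% against 76.6% (slope 0.7) and 71.0% against 71.4% (slope 1.0), so no gain. Adding site as well makes 45 × 2 × 2 × 2 = 360 cells for 550 participants, about 1.5 per cell, and power falls to about 0.52-0.60.

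**Type I error.** It was 0.045-0.058 for every method in the latent-variable runs. In a separate null run of 2,500 trials it was 4.6% (CMH) and 4.5% (logistic).

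**The case against.** The strongest defence is that CMH by MDE is valid, needs no outcome model, is stated consistently in protocol and SAP, and serves endpoints that carry no formal inference. All of that stands. It also copes with rare outcomes. With about 2-6% reaching CAPS-5 0-10 in the 1,200-trial set, some logistic fits separated, so replacing CMH by plain logistic regression throughout would create a problem.

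A reader might go further than the documents and the check allow, in four ways:

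- **That all nine endpoints lose power.** A gain was found only for CAPS-5 0-22. For CGI-I and PGIC responders, SAP 9.2.1 uses no baseline term even in the continuous models, so consistency does not call for one here.
- **That the analysis should follow every allocation factor.** Three are omitted (site, sex and tobacco), but sex and tobacco add essentially nothing in these scenarios, and site as a CMH stratum costs about 20-25 power points.
- **That the reported odds-ratio intervals would narrow.** They would widen, because the adjusted odds ratio is conditional. For CAPS-5 0-22 the mean SE of the log odds ratio was 0.220 (Mantel-Haenszel) v 0.230 (logistic) at slope 0.7, and 0.215 v 0.232 at slope 1.0.
- **That the omission threatens validity.** Type I error held throughout.

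**Conclusion.** The point holds in a limited form. Leaving baseline CAPS-5 out of SAP 9.2.2 gives up a small amount of precision for CAPS-5 0-22: about 1 to 5 power points at slopes of 0.5 to 1.0, and nothing if the correlation with baseline is about 0.1 or less. Little or nothing is lost for 10-point Response, 50% improvement or CAPS-5 0-10. Loss of Diagnosis and the CGI-I and PGIC responders were not simulated.

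The size rests on an assumed effect, SD, slope, missing rate and covariate prevalences, and the entry threshold of 33 narrows the baseline range. The primary and key secondary tests are untouched. This is a desirable refinement, not an error.

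There is a separate wording mismatch. Protocol 13.4.3 speaks of "controlling for the randomization stratification of presence of current MDE" and the synopsis is similar, as if MDE were the only factor, whereas Protocol 7.1 and SAP 3.2 list four.

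**What to change.** 1. For the CAPS-5 endpoints, keep the CMH test and add baseline CAPS-5, for example as MDE by baseline tertile (2 × 3 = 6 strata), with the cut-point rule fixed before unblinding. This showed no material loss for any endpoint simulated.
2. In addition or instead, for the non-rare CAPS-5 endpoints, pre-specify a logistic model with treatment, MDE and baseline CAPS-5 (sex and tobacco optional, site left out). Report the standardised risk difference with its 95% CI.
3. Keep CMH as the lead analysis for CAPS-5 0-10, Remission and sustained Remission, where plain logistic regression can separate.
4. Reword the synopsis and Protocol 13.4.3 so that MDE is named as one of four factors in the dynamic randomisation.

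The cost is SAP wording, a protocol wording correction and a few lines of code, with no new data or participants. The downside is a little more analysis and an adjusted odds ratio that is conditional with a wider interval, so the gain will show in the test and the risk difference.
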